**Monitoring of Data Quality by the research team:**

The research team will review the following items on weekly basis to ensure data quality and completeness:

- Total enrollment compared with anticipated enrollment
- Number of ineligible patients registered
- Proportion of missing data
- Number of participants completing the study

Additionally, the research team will receive a report on safety and outcome data for the trial:

- Number and types of SAEs
- Number and types of reportable AEs

**PROTOCOL TITLE: Proof-of-Concept Trial of a Positive Psychology Intervention for Caregivers of Patients with Hematologic Malignancies Undergoing Hematopoietic Stem Cell Transplantation**

**ClinicalTrials.gov Requirements**

As per Public Law 110-85, this is an applicable clinical trial and will be registered and results will be reported with ClinicalTrials.gov. The CRC will be responsible for handling ClinicalTrials.gov requirement for this project under [name] (PI) oversight. She will work closely with the Partners Human Research Affairs QI Program to register the trial prior to enrolling the first subject. Once a record is established, she will confirm accuracy of record content; resolve problems; and maintain records including content update and modification. She will also be responsible for aggregate results reporting and AE reporting at the conclusion of the project. We will ensure that summary results will be reported to clinicaltrials.gov no later than one year after the primary completion date.

## **12.0 Withdrawal of Subjects\***

We do not anticipate any circumstances under which the subjects will be withdrawn from the research without their consent. We do not anticipate any termination of participants. When verbal informed consent is being obtained from patients, we will emphasize to participants that they can withdraw from the study at any time for any discomforts. Participants who withdraw from the study will still have their data potentially analyzed depending on when in the study they withdraw, and participants will be informed of this as well. We will ensure that contact with participants is confidential by using only the phone numbers and other contact information that are specifically allowed by the participants and not leaving study-related messages for participants unless expressly allowed by participants. Upon enrollment, we ask all participants if it is acceptable to leave voice messages on their phones, as well as the appropriate times to call them. We adhere to any and all participant requests regarding contact. If a participant requests withdrawal from the study, we will ask them if they are comfortable sharing the reason for withdrawal to ensure that there are no adverse events to report to the IRB. We will ask the study participant if they are still willing to permit the study team to continue to monitor their health record, but withdraw from all other study procedures.

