## PROTOCOL TITLE: Proof-of-Concept Trial of a Positive Psychology Intervention for Caregivers of Patients with Hematologic Malignancies Undergoing Hematopoietic Stem Cell Transplantation

patient transplant consent visit) are completed in the pre-transplant phase and to speak with the study interventionist, a trained CRC, weekly. Immediately after the completion of each exercise, participants will rate the ease of exercise completion, overall utility of the exercise, and their current levels of positive affect. After the Week 9 intervention phone session, participants in Phase-2 will repeat self-assessment questionnaires completed at baseline either over the phone, in-person at a routine clinic visit, or via a REDCap survey link emailed to participants. Additionally, participants will be asked to complete a recorded exit interview over the phone. These individual, semi-structured exit interviews will elicit feedback about the intervention (e.g., relevance and applicability of the chosen PP exercises, intervention length, timing, and delivery), study procedures, and the questionnaires. Exit interviews will be recorded, transcribed, coded and thematically analyzed. With the Oppenheimer Grants Program funding, participants who complete study procedures will receive \$100 renumeration for their time and feedback. At study completion, we will inquire about participants' potential interest in being contacted about our future studies.

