### 9.5 Data from the Electronic Health Record

## PROTOCOL TITLE: Proof-of-Concept Trial of a Positive Psychology Intervention for Caregivers of Patients with Hematologic Malignancies Undergoing Hematopoietic Stem Cell Transplantation

Since this is a caregiver study and caregivers are not patients, we will not be obtaining any patient information from the electronic health record.

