### 9.6 Data Collection

We will collect and enter all caregiver-reported data electronically using Research Electronic Data Capture (REDCap). The REDCap Survey is a tool for building and managing online surveys. Vanderbilt University, in collaboration with a consortium of institutional partners, has developed this software and workflow methodology for electronic collection and management of research and clinical trial data. Our research team has extensive experience using REDCap and will create and design the surveys in a web browser, with institutional information technology support. The REDCap Survey system offers secure, HIPAA compliant, web-based applications that provide an intuitive interface for participants to enter data, with real-time validation rules at the time of entry.

Participants will be e-mailed a remote access link to the REDCap system [Appendix S] containing questionnaires for them to complete or they can complete questionnaires during in-person clinic visits. If any participants refuse or are unable to complete the questionnaires on the computer, they will be permitted to use hard-copy paper. Participants will also be provided the option to complete questionnaires over the phone. The CRC will contact participants (in-person or via telephone) daily for two days to remind them to complete and return the surveys. If study participants fail to complete the surveys within seven days of the expected time point, we will report the data as missing and document the reason for incompleteness. Table 4 details the schedule for administering the self-report measures.

Table 4: Administration of Self-Report Measures		
Participant	Baseline	Week-9 (+ 1 week window)
Patient Measures:		
Demographics	X	
CarGOQOL	X	X
CRA	X	X
HADS	X	X
CASE-t	X	X
MOCS	X	X
Accelerometer	X	X
LOT-R	X	X
PANAS	X	X
SWLS	X	X
GQ-6	X	X
Flourishing Scale	X	X

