**Weekly phone sessions for positive psychology intervention:** All participants will be asked to complete the 9 weekly PP exercises and to speak with the interventionist weekly. Weekly phone sessions will last approximately 15-20 minutes. Prior to completing each phone session, participants will be asked to rate their current level of happiness and optimism, using a 10-point Likert scale. Immediately after completing the exercise and phone session, participants will rate the ease of exercise/session completion, overall utility of the exercise/phone session, and their current levels of happiness and optimism, all using 10-point Likert scales. These calls will be recorded so that a percentage (10%) of these recordings can be reviewed by [name], to ensure that the PP intervention is being delivered as described in the protocol. Given the results of our prior PP studies in medical populations yielding a 64-85% completion rate of the exercises, our recent proof-of-concept trial (18-225) yielding 100% completion rate among HSCT recipients, and that this is a feasibility study (i.e., we want to assess participants' willingness to complete the phone sessions), we will expect participants to complete at least 6 PP exercises. In other words, if a participant completes at least 6 sessions, missed sessions will not be considered a deviation from the protocol.

**Follow-up assessments:** At Week 9, participants will repeat self-assessment questionnaires obtained at the beginning of the study either in-person, during a routine follow-up clinic visit, over the phone, or via a REDCap survey link e-mailed to them, depending on participant's preference. A week prior to intervention completion, participants will be mailed the Actigraph GT3X+ for follow-up physical activity data collection and participants will mail back the Actigraph in prepaid envelopes we will provide. Furthermore, participants will be asked to provide feedback about the program via a recorded exit interview over the phone.

**Positive Psychology Program Content:** All phone sessions will include (a) a review of the ease and utility of the week's PP exercise, (b) a discussion of the rationale of the next week's PP exercise through a guided review of the PP manual, and (c) assignment of the next week's PP exercise. During the calls, the interventionist and participant will also review the next section of the treatment manual and prepare for the upcoming week's exercise.

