### **24.0 Compensation for Research-Related Injury**

**PROTOCOL TITLE: Proof-of-Concept Trial of a Positive Psychology Intervention for Caregivers of Patients with Hematologic Malignancies Undergoing Hematopoietic Stem Cell Transplantation**

With the Oppenheimer Grants Program funding we will renumerate participant with a \$100 check after completing all study procedures.

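### Section 12.0 offers a withdrawing caregiver only health-record monitoring, which the study does not use, and the plan does not clearly provide for week-9 assessments once sessions stop

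*Combined protocol and SAP*

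**What the plan says.** **Withdrawal.** Section 12.0 covers a caregiver who requests withdrawal. Staff ask two things. One is the reason: "we will ask them if they are comfortable sharing the reason for withdrawal", so that any adverse event can be reported. The other is the only offer of continued participation: "We will ask the study participant if they are still willing to permit the study team to continue to monitor their health record", with release from everything else. On data already collected, the section says: "Participants who withdraw from the study will still have their data potentially analyzed depending on when in the study they withdraw". It does not say which timing counts. Section 9.5 reasons that caregivers are not patients and states that "we will not be obtaining any patient information from the electronic health record".

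**Follow-up.** Section 9.1 says: "After the Week 9 intervention phone session, participants in Phase-2 will repeat self-assessment questionnaires completed at baseline". It then adds the exit interview. Section 9.7 says: "At Week 9, participants will repeat self-assessment questionnaires obtained at the beginning of the study", and Table 4 labels the column week 9 with a one-week window. Section 9.6 adds: "If study participants fail to complete the surveys within seven days of the expected time point, we will report the data as missing", with the reason documented. The actigraph goes out again at week 8 (section 9.3), or a week before the intervention is completed (section 9.7).

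**What the data serve.** Section 8.0 puts completion of the assessment battery in the primary endpoint and lists the proportion completing assessments as a secondary endpoint. Sections 1.2 and 10.1 count a caregiver as completing the intervention at six of nine, and section 9.7 does not treat missed sessions as a deviation once six are done.

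**The concern.** The withdrawal question and the data the study needs do not match. Staff who follow section 12.0 exactly ask for access to a source that supplies no study variable. They release the caregiver from the three things that week 9 is meant to provide: questionnaires, actigraphy and exit interview. The section has no wording for a caregiver who wants to stop the calls but would still fill in a questionnaire.

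The two descriptions of follow-up timing add to this. Under section 9.1, a caregiver who stops after session 6 meets the completion criterion, yet has no week-9 session to set off the questionnaires. Under section 9.7 and Table 4, the same caregiver is due at week 9.

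At stake are the assessment-completion endpoint and the feedback that is to shape a later efficacy trial. People who stop early are the ones whose views on length, timing and content a feasibility study most needs to hear.

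**Working it through.** The plan gives no dropout allowance and no power figure to reproduce. Section 4.0 takes 20 for phase 2 from common practice, and section 10.2 declines a calculation. The check is therefore a comparison of the text, followed by an illustrative range.

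**1. Is the health record a data source?** Section 9.5 rules out patient information from it. The measures in section 9.3 and Table 4 are self-reports and an accelerometer; none is taken from anyone's record. The chart review in section 5.1 serves only to identify potential participants. So the one continuing source offered at withdrawal supplies no endpoint.

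**2. Who is asked for week-9 data?**

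| Caregiver | Section 9.1 | Section 9.7 and Table 4 | Section 12.0 |
|---|---|---|---|
| Attends session 9 | asked | asked | does not apply |
| Stops after session 6, does not withdraw | no trigger | due at week 9 (+1 week) | does not apply |
| Requests withdrawal | no trigger unless session 9 was held | due only if still in the study | released from all but record monitoring |

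The middle row depends on which section staff follow. The bottom row is a loss under either.

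**3. Which results need week-9 data?** Enrolment and completion of at least 6 of 9 sessions can be counted for every caregiver without it. Ease and utility are rated exercise by exercise, so ratings exist up to the point of stopping, but not for later exercises. The week-9 battery, follow-up actigraphy and exit interview are exposed, and with them the assessment-completion endpoint.

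**4. How large could the loss be?** Take N = 20, assume all start the intervention, and let x be the number who reach the week-9 session. Assume that only they are assessed and that all of them respond. Then the number missing is 20 − x, and the standard error of a week-9 mean grows by √(20/x). The interval is the exact 95% binomial interval for x/20, the method that section 10.1 names for feasibility.

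| x | x/20 | Missing | Exact 95% interval | √(20/x) |
|---|---|---|---|---|
| 13 | 65% | 7 (35%) | 40.8% to 84.6% | 1.24 |
| 15 | 75% | 5 (25%) | 50.9% to 91.3% | 1.155 |
| 17 | 85% | 3 (15%) | 62.1% to 96.8% | 1.085 |
| 20 | 100% | 0 | 83.2% to 100% | 1.00 |

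The row x = 13 matters because 12/20 is exactly 60% and fails a criterion of more than 60%, so 13 is the smallest count that passes. The trial could meet its completion criterion and still lack week-9 data on about a third of caregivers. If some of those 13 had themselves stopped at six to eight sessions, the literal reading of section 9.1 would lose more; the documents give no figure for that.

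**The case against.** The strongest reply is that the plan mostly works. Section 12.0 applies to a request to leave the study, not to missed calls, and section 13.0 lets staff postpone or end sessions on request without calling that withdrawal. The session-9 trigger appears only in section 9.1. Section 9.7, Table 4 and the seven-day rule in section 9.6 use an expected time point, and Table 1 places exit interviews at nine weeks. The numeric criteria need no week-9 data, section 10.1 specifies no pre-post analysis, and an unreturned battery is itself a feasibility result. Sections 9.7 and 11.0 report that everyone who started the previous trial finished.

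Most of this stands and limits the point. It does not remove it: no section says that a caregiver who has stopped is to be asked for week-9 data, and section 12.0 points staff elsewhere. The earlier 100% came from transplant recipients. Section 2.0 says such interventions have never been tested in their caregivers, and section 17.0 expects that some patients may die during the study or within months of completing it.

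Four stronger readings are tempting but not supported:

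- A reader might infer that outcome data will come mainly from finishers. That could apply only to the week-9 items, and only if attrition is substantial.
- A reader might turn the 64-85% in section 9.7 into 3 to 7 of 20 caregivers stopping. That figure is a completion rate of exercises, and scattered missed exercises are compatible with everyone attending session 9.
- A reader might expect assessment completion to be computed only among those who reach session 9. No section gives such a denominator; section 8.0 speaks of 20 caregivers, and section 3.1 counts withdrawals towards accrual.
- A reader might conclude from section 24.0, where payment is a "check after completing all study procedures", that a caregiver with six sessions goes unpaid. Section 9.7 tolerates missed sessions after six, and nothing says that payment would be refused.

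**Conclusion.** The point holds in a limited form. Sections 12.0 and 9.5 are at odds, sections 9.1 and 9.7 give different triggers for follow-up, and the plan does not separate stopping the sessions from leaving the study. As written, it can give up week-9 questionnaires, actigraphy and exit interviews that the caregiver might have provided.

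The loss ranges from none, if completion repeats the previous trial, to 7 of 20 if 13 finish and only finishers are assessed. Both ends are assumptions about attrition, not predictions from the documents. The enrolment and 6-of-9 results are not affected, and weekly ratings remain available up to stopping. This is worth correcting because the stated rule releases data that an endpoint needs and the remedy is small. It does not threaten the main feasibility conclusions.

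**What to change.** 1. In section 12.0, replace the health-record question with an optional request along these lines: *Would you be willing to stop the sessions but still complete the week-9 questionnaires, wear the activity monitor and take part in the exit interview?* Keep the question about the reason for withdrawal, and state which withdrawn caregivers' data are analysed.
2. Reconcile section 9.1 with section 9.7 and Table 4. Every registered phase-2 caregiver who has not refused data collection is assessed at week 9 (+1 week), or at the end of sessions if these were postponed, whatever number of sessions was completed. The second clause matters because section 9.3 describes follow-up as taking place at the end of the intervention, and a strict calendar date would survey caregivers with postponed sessions too early.
3. In sections 8.0 and 10.1, state that assessment completion is reported over all registered phase-2 caregivers.

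The cost is a few sentences in the protocol, matching words in the verbal consent script, and a few more calls or emailed links. Follow-up timing will vary somewhat between caregivers with postponed sessions and the rest, so the assessment date should be recorded. No change to the payment terms is needed for this point.

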## **13.0 Risks to Subjects\***

The risks to participating in this study should be relatively limited and is no more than minimal risk. Given this is a supportive caregiver-oncology study, we do not anticipate any study-related events meeting the FDA definition of a SAE (i.e., any fatal event, immediately life-threatening event, permanently or substantially disabling event, event requiring or prolonging inpatient hospitalization, or any congenital anomaly). This study population is comprised of caregivers of patients undergoing HSCT.

We anticipate no physical risks to participating in this study. Study participants may experience discomfort from discussing psychological experiences and could experience the evaluation as intrusive. Study participants who do not find any benefit from participation may find this upsetting. Activities to obtain data through the baseline and follow-up assessment battery may provide some inconvenience to study participants.

**Non-Serious Adverse Events:** The IRB will be provided with unblinded summaries of study related non-serious adverse events by treatment group at the continuing reviews. These reports will include types of events, severity, and treatment phase. To date, we have had very few non-serious events in our supportive care studies.

As this is a behavioral study, there are no ingested medications, and no biomedical procedures. It is unlikely

**PROTOCOL TITLE: Proof-of-Concept Trial of a Positive Psychology Intervention for Caregivers of Patients with Hematologic Malignancies Undergoing Hematopoietic Stem Cell Transplantation**

that participants will be at any risk for physical harm as a result of study participation.

**Reaction Management:** Verbal consent will be provided by each participant following the explanations by the CRC. The consent will include all study procedures, information about potential risks and benefits of participation, and information regarding whom the participant can contact for further questions. It also will state that participation is voluntary, that participants can refuse to answer any question, that they can withdraw from the study at any time, and that study participation is in no way related to their medical care. All study staff will complete the required human subjects training before working on any human subject aspects of the study.

Should a participant exhibit or express distress, they will be reassured by the study staff that they need not answer any questions they find upsetting. They will also be reminded that study participation is voluntary. If participants remain distressed, the study staff will notify both the study PI and primary transplant clinician. Should several participants express distress over an individual item, the research team will review the questionnaire and contact the IRB to consider removing it from the study.

If a participant reports severe distress or suicidal ideation during the study conduct, the CRC will inform the PI. The PI will determine the need to involve social work or psychiatry and take further action as deemed necessary. The research team will review sensitive items regarding suicidal ideation within 120 hours (5 business days) of receipt of completed surveys and will report any suicidal ideation to the PI promptly. We will take all measures to ensure that participants are comfortable, and we will postpone or end intervention sessions at study participants' requests. We will also ensure that the PI or other psychiatry study staff is available to intervene if needed (due to participant discomfort or to answer specific questions about the study), during intervention sessions and assessments. We have been thoughtful to use the briefest methods necessary to assess emotional states and other outcomes to reduce participant discomfort.

As with any study, there is the risk of a breach of confidentiality of the data collected. To minimize the potential loss of confidentiality, we will employ multiple safeguards and measures. Study procedures and intervention sessions will be administered by a trained interventionist. Study participants will be assigned a unique study identification number, stored separately from personal identification information. All data, including telephone recordings and transcripts, will be securely stored in locked file drawers. All project file cabinets and computer databases will be secured in locked offices. We will ensure to not provide any data to third parties. Data will be aggregated and summary reports will be generated without any personal identification information.

